2. First-two-passes cumulative diagnostic yield is calculated as the proportion of patients for which first-two-passes cumulative TBNA pass during the bronchoscopic procedure yielded a definitive diagnosis out of the total number of patients that have received a diagnostic procedure.
3. First-three-passes cumulative diagnostic yield is calculated as the proportion of patients for which first-three-passes cumulative TBNA pass during the bronchoscopic procedure yielded a definitive diagnosis out of the total number of patients that have received a diagnostic procedure.
4. Etc.... until the fifth pass.

The number of patients has been calculated to demonstrate an increase of the TBNA first-pass diagnostic yield by 20%, from 70% to 90%, between the Robotic-guided TBNA and the Robotic-nCLE-guided TBNA, with a statistical power of 80% with a 2-sided significance level of 0.05. A group size of 59 patients per arm has been derived. By including 59 patients in each arm, we expect to image at least 29 malignant nodules (prevalence of 0.5) in each arm.

The study will enroll 118 consecutive patients randomly assigned 1:1 to Robotic-guided TBNA arm or Robotic-nCLE-guided TBNA arm.

5. Treatment of Subjects

Investigational product/treatment

In recent years, confocal laser endomicroscopy (CLE) has emerged as a novel technique that enables *in vivo* microscopic analysis during ongoing endoscopy [24]. CLE is based on tissue illumination with a low-power laser with subsequent detection of the fluorescence light reflected from the tissue. It is a contrast-based technique, the most widely used agent being the intravenously administered fluorescein. The probe of the endomicroscopy system consists of a flexible catheter probe representing a bundle of optical fibers linked to a micro-objective, a laser scanning unit, and the control and acquisition software (Cellvizio® I.V.E system, Mauna Kea Technologies, France). The principle of the technique is based on a laser beam of the defined wavelength being focused towards the targeted tissue, and the recaptured signal is displayed as 'optical biopsies' in a single horizontal plane.

[figure not shown]

Figure 1: A- Locking of the CLE probe to the aspiration needle. B- CLE probe inside endosonography needle. C- Endosonography images of n-CLE measurements (white arrow) inside a lymph node (LN) (Wijmans/Annema et al. [10]).

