nCLE requires the administration of exogenous fluorescent contrast. Minutes before CLE positioning, the patient will be administered 2.5 mL of 10% fluorescein IV. A repeat dosage of 2.5 ml of 10% fluorescein can be provided after 15-30 minutes to a maximum dosage of 5 ml of 10% fluorescein in total. Patients will be monitored for allergic reactions, including anaphylaxis. Fluorescein Sodium can be used as a contrast agent with Cellvizio® I.V.E system with Confocal Miniprobes™ without change of formulation, mode of action, approved dose, or route of administration. Refer to the indications for using the fluorescein to perform the injection or to chapter 1: "Fluorescein Angiography: Basic Principles and Interpretation" of Ryan et al. book on Optical Imaging Technologies [25].

The target area will then be identified on the ultrasound and/or fluoroscopy monitor and accessed in the usual manner per standard of care. Once the nodule is localized, an 18G needle with the Confocal Miniprobe™ inside will be introduced through the bronchoscope's working channel and advanced into a lung nodule. After the puncture, the AQ-Flex™ 19 N Confocal Miniprobe™ will then be advanced through the needle into the nodule. Imaging will take place, which will be evaluated by the physician performing the procedure. The on-site image interpretation will be recorded. The AQ-Flex™ 19 N Confocal Miniprobe™ will be removed, and tissue will be aspirated at the imaging site from the tip of the needle that is still in place. ROSE will be performed by the cytology team per standard of care. If no lesional tissue is identified, then the robot may be repositioned for additional needle passes. For each needle pass, a separate CLE movie will be recorded. Multiple needle passes and nCLE imaging may occur, specifically if no tumor is identified on ROSE. In the case of re-localization of the needle, nCLE imaging may be repeated before further needle aspirations. Duration will be recorded after each pass. Chest ultrasound or fluoroscopy will be performed to evaluate for pneumothorax.

7. Puncture the identified target lesion with the needle per standard of care and usual procedure (the Confocal Miniprobe™ is pre-loaded but retracted)	8. Maintain the needle as straight as possible and parallel to the working channel of the scope. (to limit the retraction of the probe within the working channel) Twist the locking device and the probe back onto the needle
	

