Suppose a patient suspected of lung cancer has a negative result of the bronchoscopic procedure. In that case, a surgical procedure (mediastinoscopy or lobectomy/pneumectomy with lymph node dissection) could follow to obtain tissue. This surgical procedure will be performed regardless of the result of nCLE imaging. If a surgical procedure is indicated, we will collect the histological images to compare with nCLE imaging. This study will not interfere with the standard cytology or the standard histology process. Digital copies of the cytological and histological slides of the measured nodules will be obtained and compared with the frames of the nCLE sequences.

Final Diagnosis or Definitive Diagnosis

For this 12-month analysis, pathology results of Robotic-aided biopsy samples that will be diagnostic of a non-malignant condition or indeterminate will be referred to as negative for malignancy or negative for brevity. Follow-up will be conducted to determine the final diagnosis (malignant or non-malignant). All cases will be followed according to the practitioner's judgment and standard of care testing (e.g., surgical tissue biopsy, repeat Robotic, CT-guided transthoracic needle biopsy or aspiration (TTNA), serial CT imaging, and lung health visits). Cases with subsequent diagnostic tests confirming a non-malignant diagnosis or without lesion progression on radiographic follow-up will be considered true-negative at 12 months, consistent with prior Robotic studies. If the follow-up diagnostics reveal malignancy or lesion growth on repeat imaging with appropriate follow-up diagnostic testing, this will be considered a false-negative. The following will also be regarded as false-negative: death due to lung cancer within 12 months; treatment without a confirmed diagnosis; and new diagnosis of cancer in the lung from any site (including non-index lesions or lymph nodes diagnosed as malignant by linear bronchoscopy during or after the index procedure).

Twelve-month diagnostic yield will be calculated per subject as the rate of true-positives (for malignancy) plus true negatives (for malignancy) of all subjects with attempted lung lesion biopsies.

Adverse Events

Definitions

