The tumor board will determine intermediate diagnosis and management recommendations for each patient at the intermediate and final diagnosis phases (see Figure 3). Three therapeutic management options will be considered: "neither treatment nor follow-up", "follow-up", or "treatment" (see above). If the diagnosis is certain, "neither surgery nor surveillance" will be recommended for benign nodules; treatment will be recommended for malignant lesions; either treatment or follow-up will be recommended for indeterminate nodules.

An intermediate diagnosis and an intermediate management recommendation will be provided after the tumor board receives TBNA histological results and recorded in the Case Report Form for each patient of both arms.

A final diagnosis and a final management recommendation will be provided just after the final diagnosis results are received by the tumor board and recorded in the Case Report Form for each patient of both arms.

These intermediate diagnosis and management recommendations will also be compared to the definitive diagnosis and final patient management decisions.

7. Statistical Analysis

Population demographics comparison in both arms:

Statistical analysis will be performed to compare the patient population in terms of demographics to assess whether there are any differences between the populations of the two arms in terms of age, sex, race, type of lung cancers, and cancer prevalence.

Lesion characteristics comparison in both arms:

Statistical analysis will be performed to compare the lesion characteristics to assess whether there is any difference in lesion characteristics between the two arms, in terms of size, location of the nodule, Presence of bronchus sign on computerized tomography, lung zone, positive PET, associated lymphadenopathy, distance closest to fissure, distance from lesion to pleura, and pre-procedure probability of malignancy.

Navigation Accuracy

Distance between the tip of the locatable guide/nCLE Confocal MiniprobeTM and the targeted lung lesion will be measured for each nodule. The median and standard deviation of the distance will be calculated for both arms. Using a statistical test (Student T-test), they will be compared between arms (Robotic-guided TBNA and Robotic-nCLE-guided TBNA).

Navigation success

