- 3) the continuous movement of a part of the cells in one direction ('directional streaming')

These criteria will be evaluated qualitatively.

New nCLE characteristics in malignant and benign lung lesions could also be identified during this study. An imaging atlas of nCLE images will also be built for the different tumor types on in-vivo characteristics. The department of pathology will be strongly involved in this project.

nCLE-video images will be reviewed and diagnosed retrospectively, independently, and blindly by investigators, expert readers, and pathologists.

The diagnostic yield will be tested to give the likelihood that nCLE will provide the information needed to establish a diagnosis.

Correlation analysis will also be performed between:

- nCLE imaging results and digital images of cytological or histopathological results
- nCLE imaging results in different tumor types.

8. End Points

Primary endpoint: The definitive diagnosis will serve as the reference standard for the calculation of study endpoints. The study pathologists will not be aware of nCLE results. The primary endpoint of this study will be the first-pass diagnostic yield, as defined in the section "Sample size calculation", i.e. and is calculated as the proportion of patients for which first-pass TBNA during the bronchoscopic procedure yielded a definitive diagnosis out of the total number of patients that have received a diagnostic procedure

Secondary endpoint: The secondary outcome of this study will be the per-patient diagnostic yield, calculated as the proportion of patients in whom the bronchoscopic procedure yielded a definitive diagnosis out of the total number of patients that have received a diagnostic procedure.

Third endpoint: The third endpoint for patient management will be assessing the clinical impact of nCLE by determining the proportion of patients with a correct change in definitive diagnosis and the associated change in management plan with nCLE.

First-pass diagnostic yield:

The study is designed to enroll 118 patients who will be randomly assigned 1:1 to Robotic-guided TBNA alone or Robotic-nCLE-guided TBNA for a statistical power of 80% with a 2-sided significance level of 0.05 to detect an increase of the primary study endpoint (per pass TBNA diagnostic yield) of at least 20%, from 70% to 90%, between the Robotic-guided TBNA and the Robotic-nCLE-guided TBNA.

Per patient diagnostic yield (cumulative pass diagnostic yield) and performance:

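### For nodules with a non-malignant or indeterminate biopsy, the plan does not keep the nCLE read out of the final diagnosis against which nCLE is scored

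*Combined protocol and SAP*

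**What the plan says.** **Role of the final diagnosis.** Section 8 makes the definitive diagnosis the reference standard for the study endpoints. Section 7 scores the cumulative nCLE and ROSE passes against it. Under Sample size calculation (Section 4), a TBNA counts as successful only if histology confirms a diagnosis that matches the final one.

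**How it is reached.** Under Final Diagnosis or Definitive Diagnosis (Section 5), non-malignant and indeterminate biopsies are called negative and resolved by follow-up: "All cases will be followed according to the practitioner's judgment and standard of care testing". Fixed outcome rules then apply. A confirmed non-malignant result or no radiographic progression at 12 months is a true-negative. Later malignancy, lung cancer death and treatment without a confirmed diagnosis are among the false-negatives.

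**Who provides it.** Section 6, Diagnostic and Therapeutic Management: "A final diagnosis and a final management recommendation will be provided just after the final diagnosis results are received by the tumor board".

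**Who knows the nCLE result.** Section 5, Steps during the procedure: "Imaging will take place, which will be evaluated by the physician performing the procedure". That on-site interpretation is recorded. The paragraph on intra-procedure interpretation adds that the bronchoscopist judges whether malignancy is present. This happens in one arm only.

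**What nCLE may change.** The third endpoint in Section 8 is the "proportion of patients with a correct change in definitive diagnosis and the associated change in management plan with nCLE".

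**Safeguards stated.** Study pathologists are unaware of nCLE results (Section 8). The offline video raters are blinded. Positive cytology or histology is itself the reference for the nCLE images. Surgery after a negative bronchoscopy goes ahead whatever nCLE showed (all Section 5).

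**The concern.** A test should not help to decide the reference that judges it. Here the nCLE call is known to the operator on the day of the procedure, while the reference for a biopsy-negative nodule is settled over the following 12 months by discretionary work-up. Nothing in the plan separates the two.

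Two routes follow from the plan's own outcome rules:

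- A benign-looking nCLE read may lead to less testing. If imaging then shows no progression, the nodule is labelled true-negative and the nCLE read is scored correct.
- A malignant-looking read may prompt treatment without tissue proof. The plan counts that as a false-negative biopsy, which implies a malignant reference. nCLE is again scored correct, although nothing independent confirmed it.

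At stake are mainly nCLE sensitivity, specificity, PPV and NPV. To a lesser degree the between-arm comparison of yield is exposed, because true-negatives enter yield and only one arm has nCLE.

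**Working it through.** **1. Which measures use the final diagnosis.** nCLE and ROSE accuracy use it directly, and yield uses it through the match with the final diagnosis and through the true-negatives. Safety, imaging and mechanical feasibility, navigation and observer agreement do not.

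**2. Where the stated safeguards reach.**

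| Step | Protection from nCLE stated? |
|---|---|
| Reading of cytology and histology | Yes, pathologists unaware of nCLE |
| Positive cytology or histology | Yes, it is itself the reference |
| Surgery after a negative bronchoscopy | Yes, regardless of nCLE |
| Repeat biopsy, TTNA, serial CT | No |
| Decision to treat without confirmation | No |
| Assignment of the 12-month label | Not stated |

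**3. How many nodules are exposed.** The plan assumes a malignancy prevalence of 0.5. In the nCLE arm 59 × 0.5 = 29.5, so about half of the nodules should be non-malignant. Unless the biopsy is falsely positive, all of these fall in the follow-up group, together with any malignant nodules that the biopsy missed. Some will later get tissue; the documents do not say how many.

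**4. Illustration for nCLE accuracy (all inputs assumed).** Let u be the share of the 59 nodules without tissue proof at 12 months, e the share of those in which the nCLE call is wrong, and r the share of those wrong calls for which the reference follows nCLE. The rise in apparent accuracy is u × e × r.

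- Low: 0.10 × 0.10 × 0.5 = 0.005, or 0.3 of 59 nodules.
- High: 0.30 × 0.30 × 0.5 = 0.045, or 2.7 of 59 nodules.

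With r = 0 the effect vanishes; with r = 1 it doubles. The formula allows movement in one direction only, so its sign is an assumption and not a finding. For scale, the cited nCLE study reports 90% accuracy in tumors. With n = 59 the 95% half-width is 1.96 × √(0.9 × 0.1 / 59) = 0.077, or 7.7 points.

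**5. Illustration for the primary comparison.** The plan's sample size comes first: a yield change "from 70% to 90%, between the Robotic-guided TBNA and the Robotic-nCLE-guided TBNA", "with a statistical power of 80% with a 2-sided significance level of 0.05". With unpooled variances, n = (1.960 + 0.842)² × (0.7 × 0.3 + 0.9 × 0.1) / 0.2² = 58.87, so 59 per arm, which agrees with the plan.

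Now suppose that reference error shifts the nCLE-arm yield by 2, 5 or 10 points (59 × 0.02 = 1.2, 59 × 0.05 = 3.0, 59 × 0.10 = 5.9 patients). Exact two-sided chi-squared results at 59 per arm are:

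| Shift | Rejection rate if both true yields are 70% and the shift favours nCLE | Power if true yields are 70% and 90% and the shift goes against nCLE |
|---|---|---|
| None | 5.2% | 80.5% |
| 2 points | 5.9% | 69.5% |
| 5 points | 9.6% | 51.1% |
| 10 points | 24.6% | 24.6% |

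The shifts are assumed. The table shows how sensitive the comparison is, not how large the bias will be.

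**The case against.** The strongest reply is that the reference is largely rule-based. Positive tissue settles the matter, pathologists are masked, and biopsy-negative cases follow listed outcomes, not free opinion. This stands, and it confines the problem to nodules with a non-malignant or indeterminate biopsy. It does not remove the problem, because the rules act on whatever work-up was chosen.

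A reader might infer that the tumor board is unmasked. The documents do not say so. They say nothing either way, and Section 6 can be read to mean that the board records results it receives. It also refers to Figure 3, which is not visible in the text reviewed. If the board only records, Section 5 leaves the person who assigns the label unnamed and masking is still not stated.

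The third-endpoint wording may simply be loose, since Section 6 plans to compare intermediate with definitive diagnoses. That is possible. As written, however, it lets nCLE change the diagnosis that serves as reference, and the correctness of such a change cannot then be judged independently.

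Finally, masking the label does not mask the work-up behind it, and a board that saw nCLE at the intermediate stage is not truly masked later. Both points are right, and the fix has to allow for them.

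**Conclusion.** The concern holds in a limited form. Followed as written, the plan leaves nCLE free to influence the reference for its own accuracy in nodules whose biopsy is non-malignant or indeterminate, and less directly the true-negatives in yield.

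Two wider conclusions are tempting but not supported. The first is that every endpoint is compromised. Section 8 uses general wording, but safety, feasibility, navigation and observer agreement do not rest on the final diagnosis. The second is that the bias always favours nCLE. For nCLE accuracy it would tend to. For arm-level yield the direction is open: fewer tests after a benign-looking read could add true-negatives, whereas treatment without confirmation counts as a false-negative and lowers that arm's yield. First-pass success also needs histological confirmation, which limits the effect on the primary endpoint.

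The documents give no size. The 0.5 to 4.5 points for nCLE accuracy, and the shifts used for the primary comparison, rest wholly on assumed inputs. The sample size is not affected. This is a gap worth closing because closing it is cheap before final diagnoses are assigned and hard to repair afterwards.

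**What to change.** 1. State that the 12-month malignant or non-malignant diagnosis is assigned by the existing Section 5 rules from pathology, imaging and follow-up only. Arm and nCLE reads are left out of the case summary, and the diagnosis is locked before nCLE results are linked. Name who assigns it. If that board would already have seen nCLE at the intermediate stage, withhold the reads there too, or report that the assignment was not masked.
2. Tabulate how each final diagnosis was verified (tissue, repeat biopsy, imaging only, treated without confirmation) by arm and by nCLE call. This makes visible any nCLE influence on work-up, which masking the label cannot undo.
3. Repeat objective 5 in tissue-verified nodules as a sensitivity analysis. Getting tissue may itself depend on the nCLE read, so report this alongside the main analysis and not in its place.
4. Reword the third endpoint so that nCLE can change the intermediate diagnosis or management, but not the definitive diagnosis.

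The cost is one redacted case summary per patient, some SAP wording, and a smaller, selected sample in the sensitivity analysis. No extra procedures or patients are needed.

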- Twelve months follow-up data: repeat diagnostic procedures or new diagnoses on any lung nodule evaluated during the initial bronchoscopic index procedure, as well as healthcare utilization since the bronchoscopic index procedure (including healthcare visits, repeat bronchoscopic procedures, transthoracic biopsy, bronchoscopy, chemotherapy, brachytherapy, radiation therapy, surgical resection, and lymph node dissection).

nCLE image quality:

nCLE image quality for each nodule will be rated by the interventional pulmonologist as:

- **Very poor:** impossibility to observe any structure or criteria
- **Poor:** The observed criteria and structures are hardly recognisable and interpretable
- **Moderate:** Structures and criteria are recognisable and interpretable with close attention, but confidence in the interpretation remains low (may require replaying the sequence frame by frame)
- **Good:** Image quality is sufficient to enable an easy structures and criteria observation and interpretation (may require replaying the sequence frame by frame)
- **Very good:** criteria and structures are recognisable and interpretable very easily

Diagnostic and Therapeutic Management

Lung cancer treatment options are the following:

- **Minimally invasive surgery.** Thoracic surgeons can use minimally invasive techniques when possible, including [video-assisted thoracoscopic surgery \(VATS\)](#) and [robotic surgery](#). Surgeons remove the smallest amount of lung tissue necessary through wedge resection, sleeve lobectomy, and bilobectomy.
- **Highly targeted radiation therapy.** Radiation oncologists have access to the latest technology to carefully shape and precisely deliver radiation to the target. Targeted treatment is available through [intensity-modulated radiation therapy \(IMRT\)](#), volumetric modulated arc therapy (VMAT), [image-guided radiation therapy \(IGRT\)](#), and [proton therapy](#). These techniques reduce the risk of side effects and improve outcomes.
- **Carefully selected systemic therapy.** Mayo Clinic oncologists have access to various systemic treatments, including [chemotherapy](#), targeted therapy, and immunotherapy. Systemic treatments are selected using many factors, including the genetic makeup of your cancer cells.

[figure not shown]

Figure 3: Randomized controlled study device with two arms: Robotic-guided TBNA and Robotic-nCLE-guided TBNA with the different steps

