Per patient diagnostic yield of each bronchoscopic procedure (Robotic-guided TBNA and Robotic-nCLE-guided TBNA) will be calculated, and the accuracy of each technique using the final/definitive diagnosis as the reference. The diagnostic yield and accuracy for each method will be compared.

Patient management:

Three therapeutic management options will be considered right after the Robotic-guided TBNA or Robotic-nCLE-guided TBNA: 'neither treatment nor follow-up', 'follow-up', or 'treatment' (see section 6). If the diagnosis is certain, 'neither surgery nor surveillance' will be recommended for benign nodules; treatment will be recommended for malignant lesions; either treatment or follow-up will be recommended for indeterminate nodules.

Overall diagnostic and therapeutic management proportion differences in the two patient populations (Robotic-guided TBNA arm and Robotic-nCLE-guided TBNA arm) will be compared using a chi-square test. Differences between Robotic-guided TBNA and Robotic-nCLE-guided TBNA arms regarding the specific diagnostic and therapeutic management categories will be compared using McNemar's test.

Safety:

One of the secondary goals of the study is to evaluate the safety of Robotic-nCLE-guided TBNA in comparison to Robotic-guided TBNA. According to the validated Common Terminology Criteria for Adverse Events scale (CTCAE: https://ctep.cancer.gov/protocolDevelopment/electronic_applications/docs/CTCAE_v5.0.xlsx). The primary serious adverse event of concern is treatment-induced pneumothorax. Based on data from a recent sizeable multicentric study [27], Robotic-related Common Terminology Criteria for Adverse Events grade 2 or higher pneumothoraces (requiring admission or chest tube placement) occurred in 2.9%. The Robotic-related Common Terminology Criteria for Adverse Events grade 2 or higher bronchopulmonary hemorrhage and grade 4 or higher respiratory failure rates were 1.5% and 0.7%, respectively. Based on these results, we assume that the pneumothoraces rate among similar patients undergoing Robotic-nCLE-guided TBNA procedures will be equivalent to that study.

9. Study Benefit/Risk Ratio

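### A biopsy-negative nodule can be scored true-negative at 12 months without a scan near month 12, and unresolved cases have no class; secondary accuracy measures and 12-month yield may be overstated

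*Combined protocol and SAP*

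**What the plan says.** The rule is in Section 5, under Final Diagnosis or Definitive Diagnosis.

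- **What is negative.** Pathology results that are "diagnostic of a non-malignant condition or indeterminate will be referred to as negative for malignancy", so specific benign and indeterminate samples are pooled. Follow-up then sorts each case into malignant or non-malignant. There is no third outcome.
- **True-negative.** A case with a later test confirming non-malignancy, or one "without lesion progression on radiographic follow-up will be considered true-negative at 12 months". No scan date, number of scans or growth criterion is given.
- **Follow-up.** "All cases will be followed according to the practitioner's judgment and standard of care testing". Serial CT is one of the examples, without dates. The dated post-procedure contacts, days 7 and 30 under Follow-up of adverse events, concern safety.
- **False-negative.** "If the follow-up diagnostics reveal malignancy or lesion growth on repeat imaging with appropriate follow-up diagnostic testing, this will be considered a false-negative". Lung-cancer death within 12 months, treatment without a confirmed diagnosis, and any new cancer diagnosed in the lung also count.
- **12-month yield.** True positives plus true negatives, over all subjects with an attempted lesion biopsy.

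Section 6, Follow-up assessment, collects "Twelve months follow-up data: repeat diagnostic procedures or new diagnoses on any lung nodule evaluated during the initial bronchoscopic index procedure" and healthcare use. Imaging is recorded there as a health service, but neither the date nor the lesion size of a scan is named. Section 8, Patient management, adds: "If the diagnosis is certain, 'neither surgery nor surveillance' will be recommended for benign nodules"; Section 6 says the same. Section 8 makes the definitive diagnosis the reference standard for the endpoints.

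**The concern.** A reference standard has to say when a negative is established. Here the words about 12 months can mean that stability was seen at month 12, or that the case was classified at month 12 from whatever imaging existed. Two sites could label the same patient differently and both follow the text.

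Under the second reading, a slow-growing cancer missed by biopsy and scanned once, early, becomes a true-negative. None of the false-negative rules stops this, because each needs the cancer to be detected, treated or fatal. Patients with no scan and no confirmatory test, lost to follow-up, or dead of another cause are not assigned to any class. No-scan cases are foreseeable, because the plan recommends no surveillance for nodules judged benign with certainty.

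At stake are the sensitivity, NPV and accuracy set out in Section 7 and the 12-month yield, where each recoded miss turns from a failure into a success. There is also a cost to the technique under study: if nCLE correctly called such a nodule malignant, the wrong reference label would make that call an nCLE false positive.

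**Working it through.** **The plan's own figures.** Section 4, Sample size calculation, gives 59 per arm for first-pass yield of 70% v 90%, 80% power, two-sided 0.05. With unpooled variance: (1.960 + 0.842)² × (0.7×0.3 + 0.9×0.1) / 0.2² = 58.87, rounded up to 59. It reproduces. At the stated prevalence of 0.5, 59 × 0.5 = 29.5 nodules per arm are malignant and 29.5 benign.

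**Can an early scan look stable?** Assumptions, not from the documents: a 10 mm nodule and volume doubling times (VDT) of 300 or 400 days. Diameter = d0 × 2^(t/(3×VDT)).
- Day 90: 10 × 2^(90/900) = 10.7 mm; 10 × 2^(90/1200) = 10.5 mm.
- Day 365: 10 × 2^(365/900) = 13.2 mm; 10 × 2^(365/1200) = 12.3 mm.

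Under these assumptions early growth is below 1 mm, against 2 to 3 mm at one year.

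**Effect on the secondary measures.** Assumptions: sensitivity 70% (control) v 90% (nCLE), no false positives, and the same share u of missed cancers recoded as true-negative in each arm. The documents give no value for u, so 0, 25% and 50% are shown.
- True positives (TP): 0.7 × 29.5 = 20.65 v 0.9 × 29.5 = 26.55. Misses (FN): 8.85 v 2.95.
- Sensitivity = TP / (TP + FN(1−u))
- NPV = (29.5 + u·FN) / (29.5 + FN)
- 12-month yield = (TP + 29.5 + u·FN) / 59; accuracy is the same with no false positives.

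| u | Sensitivity, control v nCLE | Diff. | NPV, control v nCLE | Diff. | Yield, control v nCLE | Diff. |
|---|---|---|---|---|---|---|
| 0 | 70.0% v 90.0% | 20.0 | 76.9% v 90.9% | 14.0 | 85.0% v 95.0% | 10.0 |
| 25% | 75.7% v 92.3% | 16.6 | 82.7% v 93.2% | 10.5 | 88.75% v 96.25% | 7.5 |
| 50% | 82.4% v 94.7% | 12.4 | 88.5% v 95.5% | 7.0 | 92.5% v 97.5% | 5.0 |

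**When the yield difference does not shrink.** Recoding adds u × 8.85/59 = 0.15u to control yield and u × 2.95/59 = 0.05u to nCLE yield. The difference is preserved or widened once the nCLE share is at least three times the control share. With 25% v 75%: 88.75% v 98.75%, still 10 points.

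**Other sensitivities.** The 70% and 90% are first-pass yields used as stand-ins. Section 4 expects yield to rise over passes to a plateau, so cumulative sensitivities may be higher and closer together. With an assumed 85% v 92%, misses are 4.4 v 2.4 per arm, and the yield difference moves from 3.5 to 2.6 (u = 25%) or 1.8 points (u = 50%).

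**Primary endpoint.** Section 8 refers the first-pass yield back to Section 4. There a TBNA succeeds only with histological confirmation that matches the final diagnosis, and a pass is non-diagnostic if further passes or tests are needed. An indeterminate first pass on a missed cancer is thus a failure whatever a later scan shows. Only a wrong specific-benign result could pass through.

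**The case against.** The strongest reply is that the plan does not say any scan will do. The paragraph presents itself as a 12-month analysis, lists serial CT, and dates the label to 12 months; status assessed at month 12 is a fair reading. A reader might infer a rule that accepts a scan however early. The documents do not state one: it is one reading of ambiguous text. What stands is that nothing elsewhere settles the ambiguity.

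Second, the false-negative rules are broad. A missed cancer with a stable early scan reverts to false-negative if it is found later in follow-up. Counting non-index cancers and treatment without a confirmed diagnosis can even score a benign index nodule as false-negative, which lowers NPV. A net overstatement of NPV is therefore possible, not established. The gap remains for cancers not yet detected, treated or fatal.

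Third, a reader might infer that the arm difference must shrink. It need not: follow-up is practitioner-driven, and nothing fixes equal recoding shares. The three-to-one condition above shows where shrinkage in yield stops.

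Fourth, a reader might infer that the primary comparison is diluted. That would follow only if true-negatives counted as first-pass successes. With 10% of first-pass failures recoded in each arm, 70% v 90% would become 73% v 91%, and power would fall from 80% to 75% (unpooled). The Section 4 rule does not count them so.

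Finally, imaging is already captured as a health service. That is true, and it makes the remedy cheap.

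**Conclusion.** The point holds for the secondary accuracy measures and the 12-month yield. A stated classification rule can mislabel a nodule when followed as written, and several foreseeable patient groups have no class. It can overstate sensitivity, NPV, accuracy and 12-month yield, and can count a correct nCLE call as a false positive. It may reduce the arm difference in these measures if the recoded shares are similar.

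The size cannot be derived from the documents. The illustrated losses (3.4-7.6 points of sensitivity difference, 3.5-7 of NPV difference, 2.5-5 of yield difference) rest on assumed sensitivities of 70% v 90%, prevalence 0.5 and 25-50% of misses recoded in each arm. They are smaller if cumulative sensitivities are higher and closer together. The primary first-pass yield is largely unaffected under Section 4. The change should be made, but it does not put the primary result in doubt.

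**What to change.** In Section 5, Final Diagnosis or Definitive Diagnosis, before any follow-up data are classified:

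1. Count a nodule as true-negative on imaging only if the no-progression scan falls at or after a pre-stated window around month 12. Leave the route through a confirmatory test as it is.
2. Add an *unresolved* class for nodules with only earlier scans, nodules with no scan and no confirmatory test, and patients lost or dead of other causes before the window.
3. In the main analysis, keep unresolved cases in the denominator of 12-month yield as not successful.
4. Report sensitivity, specificity, NPV, accuracy and yield by arm twice, with the unresolved cases set all malignant and then all benign.
5. In Section 6, Follow-up assessment, add two fields: date and lesion size of the last routine scan.

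This is an analysis rule. It needs no extra scan and no change to care. The cost is SAP wording and two case report form fields drawn from imaging already recorded. The downside is a slightly less favourable 12-month yield and accuracy reported as a range.
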